#### **4.2. SAFETY ANALYSIS SET**

Bleeding other than safety-related reactions will not be investigated here. Bleeding events will be evaluated using the same analysis set as effectiveness.

#### **4.3. OTHER ANALYSIS SET**

Not applicable. All eligible patients will be used for the analysis except the pre-designated sub-analysis.

#### **4.4. SUBGROUPS**

- None

## 5. ENDPOINTS AND COVARIATES

### 5.1. EFFICACY/EFFECTIVENESS ENDPOINT(S)

#### 5.1.1. Primary effectiveness endpoint and primary analyses

The following outcomes will be assessed as effectiveness endpoints. Primary endpoint is incidence of a composite of recurrent stroke (ischemic and hemorrhagic stroke)/SE in NVAF patients treated with warfarin or apixaban. The definition of “recurrent” is as follows, “once patients discharge from the hospital and become outpatients and then rehospitalized due to stroke (major reason for the hospitalization is stroke described in the DPC admission information)

[figure not shown]
[figure not shown]
1. Incidence rate (per 1,000 person-years) of a composite of recurrent stroke (ischemic and hemorrhagic stroke)/SE during the follow-up period in NVAF patients treated with warfarin or apixaban
2. Time course of proportion of the incidence of a composite of recurrent stroke (ischemic and hemorrhagic stroke)/SE-free NVAF patients treated with warfarin or apixaban (shown as two Kaplan-Meier curves, for warfarin cohort and apixaban cohort, which will be statistically compared by a Log-rank test).
3. Risk of a composite of recurrent stroke (ischemic and hemorrhagic stroke)/SE in patients treated with apixaban compared to that in patients treated with warfarin. Hazard ratio and 95% confident intervals will be calculated by a COX proportional hazard method

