8.1.1.1. Index date

The next day of the day when patients diagnosed NVAF initiate warfarin or apixaban

8.1.1.2. stroke

8.1.1.3. Defined using pre-designated ICD-10 codes (see Statistical Analysis Plan). Ischemic and hemorrhagic stroke will be included,stroke

Stroke is defined using predefined ICD-10 codes and if hospitalization for the treatment of the stroke is necessary, it will be regarded as stroke incident during the followup period.
(applicable only to the outpatients when recurrent stroke occurs)

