**2.1. STUDY DESIGN**

*It is a non-interventional comparative observational study in which patients who meet the study criteria are selected and aggregated from the patients registered in the Medical Data Vision (MDV) database.*

In this study, analyses will be conducted in a 2-step manner. The first step is an epidemiological part and the number of patients of NVAF patients with a history of stroke (cerebral infarction, cardioembolic stroke, hemorrhagic stroke or TIA) or without a history of stroke in Japan, and clinical and demographic characteristics in each cohort will be investigated. In addition, incidence rate of stroke will be investigated in each cohort and presented as incidence rates per 1,000 person-years. Relative risk of stroke/SE and major bleeding will be estimated by using Logistic regression analysis and p for interaction between OAC (warfarin or apixaban) and a history of stroke (primary or secondary) will be calculated. In this first step, propensity score matching or IPTW will not be performed to balance the patient characteristics between cohorts.

[figure not shown]
PFIZER CONFIDENTIAL

In the second step, only the secondary prevention patients who are newly diagnosed with NVAF and initiate warfarin or apixaban for prevention of cardioembolic stroke. To balance the patient characteristics between warfarin and apixaban cohorts, an IPTW methods will be applied. Using the balanced warfarin cohort and apixaban cohort, incidence of events (stroke/SE or major bleeding) (per 1,000-year) will be calculated. Additionally, Cox proportional hazard analysis will be conducted to calculate hazard ratio + 95% confident interval.

PFIZER CONFIDENTIAL

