#### 7.1.2. Patient characteristic balancing

[figure not shown]
In this study, matched cohorts (warfarin cohort versus apixaban cohort) will be created. A propensity score will be calculated based on multivariable logistic regressions in order to account for confounding effects\* and to ensure that patient characteristics will be balanced between the warfarin cohort and apixaban cohort. An inverse probability of treatment weighting (IPTW) method using the calculated propensity score will be applied. To avoid sample size inflation and to ensure appropriate estimation of variances, s-IPTW (stabilized IPTW) is used here.

Balanced (after IPTW) patient clinical and demographic characteristics will be shown. Covariate balance between apixaban and warfarin cohorts after s-IPTW will be assessed in terms of the standardized differences with a threshold of 0.1. We will present the data for each variables and standardized differences in the same table side by side to ensure that two cohorts are balanced after IPTW.

\* Covariates used for the calculation of propensity score

- Gender: male or female
- Age: absolute years
- BMI: categories BMI (kg/m^2) (<18, 18 to <22, 22 to <25, 25+, missing)
- CHADS2 score: absolute score, categories (0, 1, 2, 3, 4, 5, 6)

PFIZER CONFIDENTIAL

[figure not shown]

- CHA2DS2-VASc: absolute score, categories (0, 1, 2, 3, 4, 5, 6, 7, 8, 9)
- Treatment status of the most recent stroke before the index date (outpatient treatment, inpatient treatment, missing)
- mRS (modified Rankin Scale) at time of admission due to most recent stroke (0,1,2,3,4,5, missing)
- JCS (Japan coma scale) at time of admission due to most recent stroke (I, II, III, missing)
- ADL (Activities of daily living) at time of admission due to most recent stroke (0-19, 20-39, 40-59, 60-79, 80-100, missing)
- Duration of hospitalization due to most recent stroke
- Destination after discharge from hospitalization due to most recent stroke (1 or 5 or other (2,3,4,6,7,8,9))
- Use of tPA or urokinase for treatment of most recent ischemic stroke (thrombolytic therapy)
- Type of most recent stroke stroke (TIA, ischemic stroke, cerebral bleeding, cardiogenic thromboembolism, unknown/others)
- 

*Note: in patients with a medical history of incidence multiple stroke events, only information regarding most recent stroke (i.e., stroke event closest to the index date) will be used.*

- Comorbidities
  - Hypertension
  - Heart failure in baseline

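### The SAP's definition of a recurrent stroke requires an earlier hospital stay that the Protocol does not, so first stroke admissions in never-admitted secondary-prevention patients go uncounted

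*SAP*

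**What the plan says.** SAP 5.1.1 sets the primary effectiveness endpoint: "Primary endpoint is incidence of a composite of recurrent stroke (ischemic and hemorrhagic stroke)/SE in NVAF patients treated with warfarin or apixaban". It then defines the word *recurrent*: "once patients discharge from the hospital and become outpatients and then rehospitalized due to stroke", with stroke as the main reason for admission in the DPC admission information. The secondary effectiveness endpoints in SAP 5.1.2 use the same word.

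The Protocol's stroke definition (the text numbered 8.1.1.3) is shorter. It uses predefined ICD-10 codes, and "if hospitalization for the treatment of the stroke is necessary, it will be regarded as stroke incident during the followup period". The only condition on setting is that it is "applicable only to the outpatients when recurrent stroke occurs". No earlier discharge is mentioned.

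The cohort includes patients who may never have been admitted. SAP 4.1.1 lets TIA alone qualify a patient for secondary prevention. The propensity-score covariates in SAP 7.1.2 include "Treatment status of the most recent stroke before the index date (outpatient treatment, inpatient treatment, missing" and "Type of most recent stroke stroke (TIA, ischemic stroke, cerebral bleeding, cardiogenic thromboembolism, unknown/others". The covariate tables in both documents allow zero hospital days.

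Step 1 is worded differently. SAP 2.1 says that "incidence rate of stroke will be investigated in each cohort and presented as incidence rates per 1,000 person-years", without the word *recurrent*.

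**The concern.** Protocol 8.7 leaves detailed methods to the SAP, so the SAP sentence is the one likely to be programmed. Take a patient whose TIA or infarct was managed in clinic, who starts the drug as an outpatient and is later admitted with a stroke. If that is the patient's first hospital stay, nothing precedes it from which to be discharged, and the admission is not a rehospitalization. The Protocol counts this event and the SAP does not, so the same data give two different counts of the primary endpoint.

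At stake are the absolute rates per 1,000 person-years, which are a stated purpose of the study (SAP 2.2), and the number of events behind the hazard ratio.

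**Working it through.** **1. The two rules side by side**

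| Patient, outpatient at onset, admitted for stroke after index | Protocol 8.1.1.3 | SAP 5.1.1, literal |
|---|---|---|
| Earlier stay for stroke | counted | counted |
| Outpatient-treated stroke or TIA, earlier stay for another reason | counted | counted (the text says discharge from the hospital, for no stated cause) |
| Outpatient-treated stroke or TIA, no earlier stay of any kind | counted | not counted |

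Only the third row differs. Let f be the share of the secondary-prevention cohort with no hospital stay before a stroke admission. The documents do not give f, so I assume a range of 0 to 50%.

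**2. The SAP's sample-size table (7.2.2), reproduced**

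Inputs from the SAP are two-sided alpha 0.05, power 80%, hazard ratios 0.6, 0.7 and 0.8, and control rates 1.2 to 2.6 %/year. Maximum follow-up is 2 years (Protocol 8.1.1.7).

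Schoenfeld events: D = 4(1.960 + 0.842)² / (ln HR)². N per group = D / [(1 − e^(−2λ)) + (1 − e^(−2·HR·λ))].

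For HR 0.6 and 1.2 %/year, D = 4 × 7.849 / 0.2609 = 120.3, the two event probabilities are 0.0237 and 0.0143, and N = 3,166, as stated. For HR 0.7 and 1.2 %/year the result is 6,113 against 6,083. For HR 0.8 and 2.6 %/year it is 6,898 against 6,817. All 12 cells agree within 1.2%. The table therefore assumes a full 2 years at risk and every stroke counted.

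**3. Effect of f on rate, events and power**

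Assumptions: HR 0.65 (the SAP's expectation), 15,000 patients (the SAP says more than 15,000) split 1:1, 2 years for all, the same f in both arms, and the same underlying stroke rate in never-admitted patients as in the others.

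- Observed control rate ≈ (1 − f) × true rate, since the person-time stays in the denominator.
- Events = (1 − f) × 7,500 × (sum of the two event probabilities). At 1.2 %/year and f = 0: 7,500 × (0.02371 + 0.01548) = 294.
- Power = Φ(√(events/4) × |ln 0.65| − 1.960).

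| Control rate | f | Observed rate per 1,000 person-years | Events | Power |
|---|---|---|---|---|
| 1.2 %/year | 0 | 12.0 | 294 | 0.96 |
| | 0.1 | 10.8 | 265 | 0.94 |
| | 0.3 | 8.4 | 206 | 0.87 |
| | 0.5 | 6.0 | 147 | 0.74 |
| 2.6 %/year | 0 | 26.0 | 629 | >0.99 |
| | 0.3 | 18.2 | 441 | >0.99 |
| | 0.5 | 13.0 | 315 | 0.97 |

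The required N per group rises by 1/(1 − f): at 1.2 %/year, 4,317 at f = 0 and 4,317 / 0.7 ≈ 6,167 at f = 0.3.

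Power depends on the 2-year assumption. With 1 year of follow-up at 1.2 %/year it is 0.75 at f = 0 and 0.59 at f = 0.3. Loss of precision from weighting is ignored.

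**4. Hazard ratio**

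Uncounted events scale each arm's hazard by (1 − f), so the ratio moves by about (1 − f_apixaban)/(1 − f_warfarin). With equal f this is 1.

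**The case against.** The best defence is that the sentence was meant only to separate a new stroke admission from a continuing one. The Protocol's outpatient condition points that way. So does the major bleeding definition in SAP 5.2.1, which requires the patient to be an outpatient at onset but asks for no earlier discharge. Two figures beside the SAP definition and the code sheet are not visible and may show the intended use. This is a fair reading of intent, but the written sentence still adds a condition that the Protocol lacks.

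Four other limits stand:

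- Any earlier stay satisfies the wording, so a reader who infers that all outpatient-treated patients are shut out goes too far. Protocol 8.9 describes the source as mostly large acute-care hospitals with patients in poorer health, so f may be modest.
- A reader might infer that never-admitted primary-prevention patients cannot have the event, which would distort the Step 1 contrast and the interaction test. The documents do not support this. The rule defines *recurrent*, and Step 1 speaks of stroke or stroke/SE. The SAP text restates no event rule for Step 1, and the Protocol's rule would count a first stroke admission there.
- The proportional loss assumes equal stroke rates. If never-admitted patients have a lower rate, fewer events are lost than f suggests.
- A biased hazard ratio is not shown. Treatment status of the most recent stroke is in the propensity score, so weighting should largely balance f. A residual imbalance of, say, 0.30 on apixaban against 0.20 on warfarin would turn 0.65 into 0.65 × 0.70 / 0.80 = 0.57, but nothing in the documents indicates one.

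**Conclusion.** Wrong as written: the SAP contradicts the Protocol on the primary effectiveness event. The defect is confined to secondary-prevention patients with no earlier hospital stay of any kind, whose first stroke admission is not counted while their time at risk is. The same wording carries into the secondary endpoints that use *recurrent*.

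The main harm is to absolute rates, which fall by about f if f is equal across arms and stroke rates are equal. The size of f cannot be found from the documents. The hazard ratio is roughly unchanged under those assumptions. Power is a lesser matter: with 15,000 patients split 1:1, HR 0.65 and a full 2 years, it falls below 0.80 only near f = 0.5 at the lowest control rate. Step 1 needs its event rule stated, but a distorted Step 1 comparison or interaction is not established.

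**What to change.** Rewrite the definition in SAP 5.1.1 to match the Protocol. A stroke event is a new admission after the index date, with stroke as the main reason in the DPC admission information, in a patient who is an outpatient at onset, whether or not there was an earlier admission. A patient who is an inpatient at index must first be discharged from that stay. This keeps the likely purpose of the present wording and drops only the unneeded condition. Add a sentence to SAP 2.1 or 7.2.3 that the same stroke rule applies in Step 1 to both cohorts.

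The Protocol's stroke definition already lacks the prior-discharge condition and needs no change on that point. The cost is two sentences in the SAP, made before the endpoint is programmed. The DPC fields are the same and no new data are needed.

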### 4. ANALYSIS SETS/POPULATIONS

#### 4.1. FULL ANALYSIS SET

##### 4.1.1. Inclusion criteria

*Patients must meet all the following selection criteria*

1. *Patients registered in the MDV database 2008 through 2021.*
2. *Patients newly diagnosed with non-valvular atrial fibrillation*
3. *Patients who started anticoagulation treatment with either warfarin or apixaban after diagnosis of NVAF*
4. *Age 20 years or older on the index date*
5. *Patients who have a history\* of stroke (cerebral infarction, cardioembolic stroke, or hemorrhagic stroke) or TIA before the index date are inclusion criteria only for secondary prevention cohort, otherwise patients will be included in the primary prevention cohort.*

\* A history of stroke is checked as far back as possible from the INDEX DATE to see if there is a history of stroke. That is, the period is from the date each patient first appeared in the MDV database to the day before the index date.

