#### **4.1.2. Exclusion criteria**

*Patients who meet the following exclusion criteria will be excluded from this study*

1. *Patients with a diagnosis of valvular AF (standard disease code: 8846941), postoperative AF (8847772), AF associated with mechanical valve malfunction (T82.0), mechanical complication of heart valve prosthesis (T82.0), or rheumatic AF (I05-I09) during the baseline period\*\*.*
2. *Patients with a diagnosis of VTE during the baseline period*
3. *Patients who are prescribed any anticoagulant during the baseline period.*
4. *Patients who are prescribed anticoagulants other than warfarin and apixaban on the index date*
5. *Patients who were hospitalized for more than 6 months (including index date) regardless of reason for hospitalization.*

*\*\*: maximally 6 months prior to the index date. If sufficient patient information is available for the analysis, patients who cannot have a 6-month baseline period will be included in the analysis.*

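### The definition of a recurrent stroke has no minimum interval or new-event condition, so a readmission for the qualifying stroke can count as a primary effectiveness event, and no planned analysis would show it.

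*SAP*

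**What the plan says.** **What makes an event recurrent.** SAP 5.1.1 defines it by sequence: "once patients discharge from the hospital and become outpatients and then rehospitalized due to stroke". The one condition on that admission is that the "major reason for the hospitalization is stroke described in the DPC admission information". Protocol 8.1.1 (stroke definition) uses predefined ICD-10 codes and says that "if hospitalization for the treatment of the stroke is necessary, it will be regarded as stroke incident during the followup period", a rule "applicable only to the outpatients when recurrent stroke occurs".

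**How close the qualifying stroke can be.** The footnote to SAP 4.1.1 says that for stroke history "the period is from the date each patient first appeared in the MDV database to the day before the index date". Protocol 8.1.1.1 sets the index date as "The next day of the day when patients diagnosed NVAF initiate warfarin or apixaban". The qualifying stroke may therefore be dated as late as the day the drug is started.

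**Who is excluded for a hospital stay.** SAP 4.1.2, item 5, removes "Patients who were hospitalized for more than 6 months (including index date) regardless of reason for hospitalization". Protocol 8.2.2, item 5, is different: it removes patients in a continuous stay caused by a first stroke or another serious illness, with no limit on length.

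**Adjustment and checks.** The propensity score list in SAP 7.1.2 describes the latest stroke by type, severity, discharge destination and "Duration of hospitalization due to most recent stroke". Time from stroke to index is not on the list. SAP 7.2.1 plans one sensitivity analysis, an E-value for unmeasured confounding.

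**The concern.** The definition asks whether the patient went home and came back with stroke as the reason. It does not ask whether the stroke is new. A patient discharged from the qualifying stroke and later admitted again to continue its treatment can meet every stated condition.

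Under the SAP's exclusion, a patient can start the drug during the qualifying admission and go home during follow-up, so such a readmission can fall in time at risk. It would then do two things. It would count as an outcome, and, because a stroke ends observation under Protocol 8.1.1.7, it would hide any later true recurrence.

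At stake are the incidence rates, which are the first primary analysis listed in SAP 5.1.1, and the primary hazard ratio. An E-value deals with confounding and is silent on events that are misclassified.

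**Working it through.** **1. Does any stated rule remove such a readmission?**

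| Rule | Removes | Leaves |
|---|---|---|
| Outpatient status first (SAP 5.1.1, Protocol 8.1.1) | Direct transfers | Readmission from home |
| Stroke is the main reason (SAP 5.1.1) | Incidental stroke codes | Readmission for the same stroke |
| Hospitalised for treatment (Protocol 8.1.1) | Admissions for other purposes | Continued treatment of the same stroke |
| ICD-10 list (SAP Appendix 3) | Unknown; the sheet is not in the text | A readmission with the same stroke code as before |
| Stay over 6 months (SAP 4.1.2) | Very long stays | Shorter qualifying stays |

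No visible rule separates an old stroke from a new one.

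**2. Reproduce the plan's own figures (SAP 7.2.2).** Inputs: two-sided alpha 0.05, power 80%, and a maximum of 2 years at risk (Protocol 8.1.1.7). Allocation of 1:1 is assumed.

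- Events: D = 4(1.960 + 0.842)² / (ln HR)².
- n per group = D / (p0 + p1), with p0 = 1 − exp(−2λ) and p1 = 1 − exp(−2λ·HR).

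For HR 0.6 and λ = 0.012: D = 120.3, p0 + p1 = 0.02371 + 0.01430 = 0.03801, and n = 3,166, which is the tabulated value. All 12 cells agree within 1.2%. The table is sound. At the SAP's expected HR of 0.65 and 1.2%/year, the same method gives 4,317 per group.

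**3. Effect of false events at equal rates in both arms.** Let f be the share of counted warfarin-arm events that are readmissions for the qualifying stroke. The documents do not give f; every value below is an assumption. With true warfarin rate λ, the false rate is c = λf/(1 − f), added to both arms. Then

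HR observed = (0.65λ + c)/(λ + c) = 0.65(1 − f) + f.

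At λ = 12 per 1,000 person-years and f = 20%: c = 3.0, the rates are 15.0 and 10.8, and the ratio is 0.72.

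Power = Φ(½√D·|ln HR| − 1.96), with D the events expected from the 15,000 patients in SAP 7.2.2, taken as 7,500 per arm with a full 2 years at risk.

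| f | Warfarin rate | Apixaban rate | HR | n per group | Events | Power |
|---|---|---|---|---|---|---|
| 0 | 12.0 | 7.8 | 0.65 | 4,317 | 294 | 0.96 |
| 10% | 13.3 | 9.1 | 0.685 | 4,939 | 333 | 0.93 |
| 20% | 15.0 | 10.8 | 0.72 | 5,714 | 382 | 0.89 |
| 30% | 17.1 | 12.9 | 0.755 | 6,708 | 444 | 0.84 |
| 40% | 20.0 | 15.8 | 0.79 | 8,036 | 527 | 0.77 |

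At 2.6%/year, power is still 0.94 at f = 50%. If the tabulated 1.2%/year is instead read as the counted rate, false events included, power at f = 10, 20 and 30% is 0.91, 0.82 and 0.70; at 2.6%/year it is 0.95 or more over that range.

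**4. Unequal rates.** Let k be the apixaban-to-warfarin ratio of false-event rates. Then HR observed = 0.65(1 − f) + fk, a shift of f(k − 0.65). At f = 20%:

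| k | 0.5 | 0.65 | 0.8 | 1 | 1.25 |
|---|---|---|---|---|---|
| HR | 0.62 | 0.65 | 0.68 | 0.72 | 0.77 |

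Below k = 0.65 the estimate moves away from 1. With a true HR of 1, f = 20% and k = 0.5, it is 0.8 + 0.2 × 0.5 = 0.90, an effect that does not exist.

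These sums treat rates as constant over follow-up. If false events cluster early, the hazards are not proportional and the Cox estimate is only roughly this ratio.

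**The case against.** The strongest reply is that the problem may be small or already handled. The ICD-10 sheet is not in the text, and two figures that directly follow the definition are not shown; either may remove sequela codes or depict an interval. The Protocol requires hospitalisation for treatment, so rehabilitation or a planned procedure would not clearly qualify, and the documents do not say how DPC data code such stays. Direct transfers fail the outpatient condition. Protocol 8.9 says that care at another hospital is not seen. Protocol exclusion 5 could remove many patients who start the drug during the qualifying stay. Stroke history goes back to the first database record, and a remote stroke is unlikely to cause such a readmission.

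All of this stands as a limit on size. It is why the point is that such readmissions *can* be counted. It does not close the gap: a code list cannot tell old from new when both admissions carry the same code, and the two versions of exclusion 5 conflict.

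A reader might infer three stronger things that the documents do not support:

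- **That every stroke readmission counts and many patients are affected.** No figure supports this, and the conditions above narrow it.
- **That the hazard ratio is certainly pulled towards 1.** That needs similar false-event rates in both arms.
- **That the study loses its power.** At f = 10, 20 and 30% the events *needed* rise by (ln 0.65/ln HR)² = 1.30, 1.72 and 2.35, but false events also add to the events *observed*. On the first reading in step 3, n per group rises by only 1.14, 1.32 and 1.55.

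It is also fair to say that 30 days is a chosen window. It is not derived from the documents and would miss later readmissions for the same stroke.

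**Conclusion.** The point holds as a minor one. As written, SAP 5.1.1 read with Protocol 8.1.1 lets a readmission for treatment of the qualifying stroke count as a primary effectiveness event, and nothing planned would show whether this happens.

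Such events would inflate the incidence rates in any arm where they occur. With a true hazard ratio of 0.65 and equal false-event rates, a share of 10, 20 or 30% of warfarin-arm events gives 0.69, 0.72 or 0.76. If the rates differ by arm, the direction is not fixed, and time from stroke to index, a plausible source of such a difference, is not in the propensity score.

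The shares and ratios are assumptions. The power figures rest on a 1:1 split and a full 2 years at risk; censoring at discontinuation would lower them all. Within the 10 to 30% range, power falls below 0.80 only at the lowest tabulated event rate and only if that rate already includes the false events. The main concern is therefore bias in the rates and the hazard ratio.

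**What to change.** Keep the primary definition. Add to SAP 7.2.1 one pre-specified sensitivity analysis that repeats the primary effectiveness Cox model and incidence rates and does not count:

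- a stroke admission within 30 days of discharge from the qualifying stroke admission, or within 30 days of the qualifying stroke date if that stroke was treated as an outpatient;
- a stroke admission recorded as planned, if the data carry that field.

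Patients with a discounted admission stay in follow-up, so that a later stroke can still be counted. Report the number of reclassified events by arm; this shows both the size of the problem and whether it differs between the drugs.

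Separately, reconcile exclusion 5 in Protocol 8.2.2 with exclusion 5 in SAP 4.1.2, since they decide differently whether patients still in hospital for the qualifying stroke enter the cohort.

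The cost is one further run of the primary model, using dates the primary definition already needs. The downside is that some genuine early recurrences are not counted, in the sensitivity analysis only.
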